## Background

Schizophrenia is a serious mental disorder that has a lifetime population risk approaching 1%. In the U.S., schizophrenia affects approximately 2.4 million individuals. It typically begins in early adulthood and is a major cause of disability. Age-specific all-cause mortality rates in schizophrenia are more than 3 times greater than in the general population. Outcomes of schizophrenia are variable, ranging from slight to severe disability. For affected individuals and their families, schizophrenia can be devastating. Many people with schizophrenia have substantial social and functional impairments that contribute to high rates of homelessness, unemployment, disability, and incarceration. Globally, schizophrenia is the 5th leading cause of years lost to disability for men and 6th leading cause for women.

Antipsychotic medications are a cornerstone of schizophrenia treatment. However, because most people with schizophrenia respond only partially or not at all to an antipsychotic medication, these medications are changed frequently and combined or different classes of psychotropic medication are added. Preliminary analyses of national Medicaid data from 2001-2005 revealed that in the year before starting a new antipsychotic, most patients with schizophrenia fill a prescription for an antidepressant (67.3%), a benzodiazepine (53.2%), or a mood stabilizer (55.8%). The FDA has not approved any of these classes of drugs to treat schizophrenia, although strong evidence supports their use for the conditions for which they have been approved. Evidence is scarce for effectiveness of these medications in people with schizophrenia.

This investigation will address key patient-centered questions about medication strategies for individuals with schizophrenia who face common clinical situations, for example:

- “I have schizophrenia and take an antipsychotic drug but still have symptoms that interfere with my daily life.”
- “I have schizophrenia and take an antipsychotic drug but often feel depressed.”

In these scenarios, a doctor may recommend a medication change. Patients want to know: “What are my options? Which will best keep me out of the hospital so that I can keep my housing and job? Which will help me to lead a long life? Which choice will help me avoid the emergency room? I’m worried about side effects—which option will help me avoid serious heart problems? Or diabetes?”

A physician working with an individual with schizophrenia might have the following questions:

- What is the best medication to recommend for a person with schizophrenia who is not feeling better with just an antipsychotic?
- What is the best medication to recommend for this person who has now developed depression? Or anxiety? Or manic symptoms?

This will be the largest study of treatments for schizophrenia ever conducted. By conducting rigorous analyses using 10 years of national Medicaid data, the study will provide information to help make personalized treatment choices that fit an individual’s clinical situation and preferences with the goal of achieving outcomes that matter to the patient.

## Goal

More than half of individuals diagnosed with schizophrenia have an incomplete response to a prescribed antipsychotic medication. In spite of the high proportion of patients who experience an incomplete response, little is known about the comparative effectiveness of treatment options that are commonly used in this situation. The proposed research question “For patients with schizophrenia who have persistent, emergent or recurrent psychiatric symptoms in spite of antipsychotic treatment, what are the medication treatment options and what are their comparative benefits and risks?” thus has considerable public health importance is relevant to a large proportion of the approximately 3 million individuals with schizophrenia in the U.S. specifically, the project seeks to achieve the following aims:

1. Within five clinically important schizophrenia subgroups, compare the effectiveness and safety of alternative medication strategies beyond antipsychotic monotherapy.
2. Within the five subgroups, explore whether the comparative effectiveness and safety of alternative treatment strategies varies according to patient age and presence of a substance use disorder.
3. Conduct instrumental variable and sensitivity analyses to examine the robustness of the treatment effectiveness results that are based on propensity score methods.

The project will yield unbiased, generalizable, and patient-centered information on the comparative effectiveness and safety of alternative medication strategies for patients with schizophrenia who have an incomplete response to

standard antipsychotic monotherapy. New information will be generated regarding the comparative effectiveness and safety of commonly used but poorly understood second-line medication treatment strategies. We will compare the effectiveness of these medication treatment strategies for schizophrenia in five subgroups based on presenting symptoms and syndromes that lead to initiation of a new psychotropic strategy: 1) schizoaffective, 2) depressive, 3) anxiety, 4) manic, and 5) uncomplicated schizophrenia.

The project is designed to address critical knowledge gaps in the comparative effectiveness of pharmacological management of patients with schizophrenia, broadly conceived to include the diagnoses of schizophrenia, early course schizophrenia (schizophreniform disorder), and schizoaffective disorder. Schizoaffective disorder, a subtype of schizophrenia characterized by psychotic symptoms and persistent mood symptoms, is often diagnosed in the Medicaid population. The pharmacologic treatment of schizoaffective disorder has not been extensively studied in controlled trials, though treatment for schizoaffective disorder shows patterns that are distinct from other schizophrenia subgroups. Symptoms of anxiety, depression, and mania also commonly occur in adults with schizophrenia. Nevertheless, clinical trials of standard pharmacological treatments for anxiety, depression, and mania routinely exclude patients with schizophrenia and related psychotic disorders. As a result, little is known about the comparative effectiveness of medication options for treating schizoaffective disorder, anxiety, depression, and mania in schizophrenia.

There is little evidence on pharmacologic treatments in schizophrenia other than antipsychotics. The first step in medication treatment for schizophrenia is generally a single antipsychotic. However, most patients with schizophrenia have an incomplete response to antipsychotic monotherapy. Switching antipsychotics is a common strategy for breakthrough symptoms, but the evidence suggests switching is more likely to affect side effects than to reduce core symptoms. The one medicine consistently shown to often work when others do not is clozapine, which has an indication for both treatment-resistant schizophrenia and for reducing persistent suicidal behaviors but is rarely prescribed. Support for adding a second antipsychotic agent, though common in clinical practice, is largely confined to case reports and open-label trials rather than double-blind clinical trials. The evidence for adding agents from different psychotropic classes is summarized in Table 1.

Current practice patterns vary widely. In our preliminary analyses, we found wide variation in prescribing of different classes of psychotropic medications to patients with schizophrenia in the year prior to initiation of a new antipsychotic medication, providing additional evidence regarding uncertainty of these treatment strategies. Across states, rates varied by 2 to 3 fold. Specifically, the initiation of benzodiazepines varied from 9.2% (Kentucky) to 29.7% (Vermont); antidepressants from 19.8% (Vermont) to 48.3% (Oklahoma); and mood stabilizers from 6.6% (North Dakota) to 18.9% (Texas). Such variation underscores deficiencies in widely accepted clinical evidence concerning these important treatment decisions.

There is no professional consensus on treatments for important subgroups with schizophrenia. Schizophrenia treatment guidelines and algorithms have concluded that there is little evidence to guide selection of pharmacologic strategies for schizophrenia beyond the initial recommendation for antipsychotic monotherapy and then for clozapine for people with treatment-resistant illness.

Although there is limited information on the clinical comparisons we propose to study, recent evidence from a Finnish observational study of psychotropic polypharmacy in schizophrenia, which used methods that are similar to those that we propose, found substantial effect sizes. In that study, for example, there was a significant increase in mortality associated with adjunctive benzodiazepine use compared to antipsychotic monotherapy and adjunctive antidepressant use was associated with markedly reduced risk of suicide.

Despite the widespread use of various combinations of classes of psychotropic medicines in schizophrenia, their comparative safety and effectiveness have not been established. By determining which options are most effective in achieving desired outcomes in specific clinical situations, this project will promote personalized, evidence-based medicine and has the potential to reduce wasteful or harmful medication management approaches. By helping doctors and patients find effective treatments earlier than by simple trial and error, this project has the potential to reduce the potential harms and inconvenience of failed medication trials, adverse effects, and unnecessary hospitalizations.

## Protocol Details

### Overview of study design

The study is a retrospective cohort study of adults with schizophrenia that will compare outcomes of new users of alternative psychotropic medication strategies using 10 years of Medicaid data. The primary comparative effectiveness analyses will focus on subgroups of patients with schizophrenia facing common clinical situations.

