### Data source and cohort identification

The data source will be national (45-state) Medicaid Analytic Extracts data (2001-2010). The cohort will consist of adults who are 18 to 64 years old and diagnosed with schizophrenia who initiate a new psychotropic medication after a period of stable antipsychotic treatment. Individuals who are 65 or older because will be excluded because they also have Medicare and receive pharmacy benefits through Medicare Part D.

Schizophrenia will be defined as  $\geq 2$  outpatient claims or  $\geq 1$  inpatient claim for schizophrenia [ICD-9-CM: 295] during 365 days of consecutive Medicaid enrollment immediately prior to the index date. Stable antipsychotic monotherapy will be defined by filled prescriptions for only one second-generation antipsychotic (excluding clozapine), and no other psychotropics, for  $\geq 90$  days immediately preceding the start of the index medication (t0). After the  $\geq 90$  days of stable treatment with a single second-generation antipsychotic, study patients will have had a change in therapy defined as (1) addition of a second antipsychotic or (2) addition of a different psychotropic drug class (antidepressant, mood stabilizer, or benzodiazepine). To ensure the patients are in active treatment there must be an active supply of antipsychotic medication on t0.

The eligibility criteria select a cohort of individuals that are likely to have schizophrenia, have received antipsychotic monotherapy prior to the index date, and are still experiencing problems for which a new psychotropic medication strategy was initiated. A 1-year period of eligibility prior to follow-up initiation ensures sufficient time to collect service use related covariates to characterize cohort members.

Patients with stable clozapine monotherapy will be excluded because clozapine is largely reserved for the most severely ill patients. Patients who implement more than one change in therapy at the index date (e.g., addition of a mood stabilizer and an antidepressant) will also be excluded.

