## Approach to confounding

Physicians make treatment choices in light of available clinical information and as a result there is a risk of confounding by clinical indication for the treatments under study. Our design minimizes confounding by indication by focusing on diagnostic subgroups. To further reduce confounding, we will control for a broad range of potentially relevant factors from claims histories. These factors will be identified in the 365-day period before drug initiation and used to calculate propensity scores. In addition we will conduct sensitivity analyses to estimate the extent of unmeasured confounding necessary to fully explain our observed findings and we will conduct instrumental variable analyses if a suitable instrument is identified.

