#### AP treatment Initiation year

2002

2003

2004

2005

2006

2007

2008

2009

Diagnostic History, past year	ICD-9-CM Codes*
Depression	293.83, 296.2x, 296.3x, 296.9x, 298.0x, 300.4x, 311.xx
Anxiety	293.84, 300.0x, 300.2x, 300.3x, 308.3x, 309.21, 309.81, 313.0x, 313.2x, 313.89
Bipolar	296.xx (not 296.2x or 296.3x or 296.9x)
Substance use disorder	291.xx, 292.xx, 303.xx, 304.xx
Moderate/severe mental retardation	318.xx
HIV	042, 043, 044, 079.53, V08
Neoplasms	140.xx-239.xx (Exclude people with malignant neoplasms 140.xx-205.xx)
Diabetes	250.xx
Obesity	270.xx
Hyperlipidemia	272.0x-272.4x, 272.7x, 272.9x
White blood cell diseases	288.xx, 289.xx (exclude neutrophil d/o 288.00-288.04, 288.09, 288.1x)
Anemia	280.xx-285.xx
Drug-related dyskinesia	333.85
Hypertension	401.xx-405.xx
Ischemic heart disease	410.xx-414.xx
Pulmonary circulation diseases	415.xx-417.xx
Cardiac dysrhythmias	427.xx
Heart failure	428.xx
Cerebrovascular disease	430.xx-438.xx
Acute bronchitis and bronchiolitis	466.xx
Chronic bronchitis	491.xx
Pneumonia	480.xx-486.xx
Emphysema	492.xx
Asthma	493.xx
Appendicitis	540.xx-543.xx
Noninfectious enteritis and colitis	555.xx-558.xx
Diverticula of intestine	562.xx
Intestinal obstruction	560.xx
Chronic liver disease and cirrhosis	571.xx
Acute & chronic pancreatitis	577.0x, 577.1x
Cholelithiasis	574.xx
Acute kidney failure	584.xx
Chronic kidney failure	585.xx

Kidney infections	590.xx
Cellulitis and abscess	681.xx–682.xx
Osteoarthritis and allied disorders	715.xx
Intervertebral disc disorder	722.xx
Fractures, all sites	800.xx–829.xx
Fracture of neck of femur	820.xx
Poisoning by psychotropic medication	969.xx
Poisonings	960.xx–989.xx
Suicide and self-inflicted injury	E950-959
Intracranial injury	815.xx-854.xx
Severe cardiovascular diseases	401.0x-404.9x, 410.xx-416.xx, 425.xx-437.xx, 440.xx-447.xx
Schizophreniform	295.4x
Schizoaffective	295.7x

---

\* x indicates inclusion of any 5th digit if available for a diagnosis code.

xx indicates inclusion of any 4th and 5th digits if available for a diagnosis code.

Medication history, past year	Drug class
Psychotropic medication	
Antidepressants	SSRI/SNRI/mirtazapine, TCA and heterocyclic compounds, MAOI, trazodone-related antidepressants, bupropion
Mood Stabilizer	lithium, primary anticonvulsant, secondary anticonvulsant
ADHD medication	psychostimulants, alpha-agonists
Anxiolytic/hypnotics	benzodiazepines, GABA agonists, other newer or older anxiolytic/hypnotic

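### The cohort is labelled as new users, but only 90 drug-free days are required within a 365-day look-back, so first starts and restarts are pooled and no analysis separates them

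*Combined protocol and SAP*

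**What the plan says.** The Overview of study design states that the study "will compare outcomes of new users of alternative psychotropic medication strategies".

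The section on data source and cohort identification sets the drug-free rule: "filled prescriptions for only one second-generation antipsychotic (excluding clozapine), and no other psychotropics, for" at least 90 "days immediately preceding the start of the index medication (t0"). The index event is then the addition of a second antipsychotic or the "addition of a different psychotropic drug class (antidepressant, mood stabilizer, or benzodiazepine"). Neither option carries a condition on earlier use of that class or agent.

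The same section requires a year of enrollment, for another purpose: "A 1-year period of eligibility prior to follow-up initiation ensures sufficient time to collect service use related covariates". The section on confounding uses that year for adjustment: "These factors will be identified in the 365-day period before drug initiation and used to calculate propensity scores". Under past-year medication history, Appendix 2 lists antidepressants ("SSRI/SNRI/mirtazapine, TCA and heterocyclic compounds, MAOI, trazodone-related antidepressants, bupropion"), mood stabilizers and anxiolytic/hypnotics including benzodiazepines. It has no entry for antipsychotics.

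Under Comparators, a new antipsychotic is the reference category unless it is not a reasonable option for a subgroup. The Sample size section lets a patient contribute more than one episode and puts distinct patients at about 70% of episodes. The Sensitivity Analyses section has no analysis with a longer drug-free period and none limited to first use.

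**The concern.** A patient whose antidepressant lapsed a little over 90 days ago and who now refills it is classed as starting a new strategy. A patient with no antidepressant fill all year is classed the same way. The two face different decisions. One resumes a drug with a known personal history, and the other tries something new because monotherapy was not enough. The Goal section asks about the second decision.

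The propensity score does not separate them. Once past-year antidepressant use is balanced, its frequency is equal across arms, but its meaning differs. In the antidepressant arm it marks a restart. In the second-antipsychotic arm it marks a class tried before and now passed over. The estimate is an average over first starts and restarts in unknown proportion.

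The antipsychotic arm is less protected. A patient who took the same second agent on days 91 to 365 also counts as a new start there, and that history is not among the listed covariates.

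At stake is interpretation. If the effect differs between first starts and restarts, the pooled hazard ratio describes neither group, and nothing planned would show it.

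**Working it through.** **1. Window left open.** The look-back is 365 days and the guaranteed drug-free period is 90 days (cohort identification section). 365 − 90 = 275, so up to 275 days of the look-back may contain use of the index class or of the same second antipsychotic.

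**2. Does the plan expect such patients?** Yes. The cohort rule removes any use of other psychotropics in the last 90 days, so a past-year flag for an add-on class can be positive only through use on days 91 to 365. Listing those flags as covariates presupposes such patients.

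**3. How common might restarts be?** No figure measures this directly. Two bear on it indirectly.
- The Sample size section counts 839 distinct patients in 1,199 benzodiazepine-initiating episodes in the depression subgroup. 1,199 − 839 = 360, and 360 / 1,199 = 30%. Read literally, 30% of these starts are repeats by the same patient. The same ratio applied to antidepressants gives 4,646 × 0.30 ≈ 1,394 episodes. The 70% is approximate, may not be specific to each class and subgroup, and some repeats may be more than 365 days apart.
- The Background says that in the year before a new antipsychotic most patients "fill a prescription for an antidepressant (67.3%), a benzodiazepine (53.2%), or a mood stabilizer (55.8"%). These patients were not selected for 90 days of monotherapy, so the figures show only that prior use is common and differs by class (67.3 − 53.2 = 14.1 points at most). They do not estimate the restart share here.

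**4. The plan's own power figures.** Method: two-sided α = 0.05, equal groups of n, pooled variance under the null. Power = Φ{[d√n − 1.96√(2p̄(1 − p̄))] / √[p₁(1 − p₁) + p₂(1 − p₂)]}. The plan gives no base rate, so rates are centred on 50%, the least favourable case.
- n = 1,534, d = 0.050 (0.475 vs 0.525): (1.958 − 1.386) / 0.706 = 0.81, power 79.1%.
- n = 839, d = 0.068 (0.466 vs 0.534): (1.970 − 1.386) / 0.705 = 0.83, power 79.6%.

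Both agree with the stated 80% to within a point. At lower base rates power is higher (91.3% for 20% vs 25% with 1,534 per group).

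**5. Cost of a 365-day drug-free restriction.** Let e be the share of add-on starters removed. It is not in the documents, so a range is shown, with the Background rates as a rough upper end. Distinct patients = 0.7 × episodes × (1 − e), with the comparator matched 1:1 at that number.

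| Depression subgroup | e | Patients | Detectable difference, 80% power |
|---|---|---|---|
| Benzodiazepine | 0 | 839 | 6.8 points |
| | 10% | 755 | 7.2 |
| | 30% | 588 | 8.2 |
| | 53.2% | 393 | 10.0 |
| Mood stabilizer | 0 | 907 | 6.6 |
| | 30% | 635 | 7.9 |
| | 55.8% | 401 | 9.9 |

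For antidepressants 0.7 × 4,646 = 3,252 patients are available against 1,534 in the reference. That match is not limited by the antidepressant arm until e reaches 1 − 1,534 / 3,252 ≈ 53%. At e = 67.3%, 1,063 remain and the detectable difference is 6.1 points. The filter would also shrink the reference arm by an unknown amount, which the table does not include.

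**The case against.** The strongest reply is that the plan does not contradict itself. It speaks of new users of strategies, not of patients who have never taken the class. The 90-day rule is stated openly and applies to every arm. A 90-day drug-free period is a legitimate choice, and past-year use of the three add-on classes is adjusted for. Given that history, comparing the addition of one class with the addition of a second antipsychotic is a coherent question. All of this stands. What remains is mainly possible effect modification by prior use, together with an antipsychotic history that is not adjusted for.

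Three stronger readings are tempting and are not supported.
- A reader might infer that restarts fall unevenly across arms. This is plausible, but no figure gives restart shares by arm, and the Background rates come from a differently selected population.
- A reader might infer that early harm and discontinuation are understated because restarters have already tolerated the drug. Yet they had no fill for at least 90 days, and some may have stopped for intolerance or failure. The direction is open.
- A reader might infer that pooling hides a real first-start effect. That would need opposing effects in the two groups, and the documents give no basis for assuming them.

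**Conclusion.** The point holds as a matter of definition and of a missing check. A 90-day rule within a 365-day look-back admits restarts. The plan's covariate list presupposes them for three classes and omits antipsychotics. No planned analysis would show whether they matter. Their number is unknown. A literal reading of the plan's patient and episode counts puts repeat starts near 30%, subject to the caveats above. No bias in the main comparison is demonstrated, in size or direction. The change is worth making because it is cheap and uses data already held, and because reporting restarts by arm would show how large the issue is.

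**What to change.** Keep the main analysis and make four changes.

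1. In the Overview of study design, state that a new user is a patient with no fill of the added class, or of the added antipsychotic, in the 90 days before t0.
2. Report by arm the share of patients with a past-year fill of the index class. For the antipsychotic arm, report past-year fills of the added agent.
3. Add to Appendix 2 past-year use of antipsychotics other than the baseline agent.
4. Add to Sensitivity Analyses a prespecified repeat of each pairwise comparison, limited to patients with no fill of either compared add-on class in the full 365 days. Where a second antipsychotic is compared, also require no past-year fill of any antipsychotic other than the baseline agent. Apply the same filter to both arms.

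The new analysis can replace the listed one that restricts to diagnoses from more than one provider, since the Subgroups section already builds that condition into the main depression, anxiety and mania subgroups.

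The cost is one filter and a rerun, with fewer patients and wider intervals in every subgroup, not only in anxiety and mania. The losses in the table are acceptable for a sensitivity analysis. A 365-day filter does not guarantee first-ever use, and the write-up should say so.
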